5.5 SAFETY ANALYSES

Evaluations of safety will be performed on the Safety Analysis Set. The incidence of AEs, out-of-normal-range laboratory safety test variables, abnormal electrodiagram (ECG) findings, out-of-range vital signs, safety MRI findings, suicidality, results of the sleep questionnaire, ADAS-cog Reliable Change Index (RCI) Alert triggered, dermatology findings, and neurological examination along with change from baseline in laboratory safety test variables, ECGs, and vital sign measurements will be summarized by treatment group.

5.5.1 Extent of Exposure

The duration of exposure to study drug will be summarized as cumulative extent of exposure in categories with 3-month increment on the Safety Analysis Set and FAS. If drug interruption occurs, then the drug interruption duration will be subtracted to calculate duration of exposure. The cumulative number and percent of subjects in each applicable exposure category will be presented by treatment group. Duration of exposure will be summarized using descriptive statistics as well as by 3-month duration categories using counts. The number and percent of subjects within each duration category will be presented by treatment group. Overall exposure (number of subject-months) is defined as summation over all subjects' exposure durations and will be summarized by treatment group.

The duration of exposure to study drug in OLE phase will be summarized on All Safety Subjects similarly.

5.5.2 Adverse Events

The AE verbatim descriptions (investigator terms from the eCRF) will be classified into standardized medical terminology using the MedDRA. AEs will be coded to the MedDRA (Version 22.0 or higher) lower level term closest to the verbatim term. The linked MedDRA PT and primary SOC are also captured in the database.

A treatment-emergent adverse event (TEAE) is defined as:

- An AE that emerges during treatment or within 4 weeks (28 days) following the last dose of study drug, having been absent at pretreatment (Baseline) or

- Reemerges during treatment or within 4 weeks (28 days) following the last dose of study drug, having been present at pretreatment (Baseline) but stopped before treatment, or
- Worsens in severity during treatment or within 4 weeks (28 days) following the last dose of study drug relative to the pretreatment state, when the AE is continuous.

Only those AEs that are treatment-emergent will be included in summary tables. All AEs, treatment-emergent or otherwise, will be presented in subject data listings.

The TEAEs will be summarized by treatment group on the Safety Analysis Set. The incidence of TEAEs will be reported as the number (percentage) of subjects with TEAEs by SOC and PT. A subject will be counted only once within an SOC and PT, even if the subject experienced more than 1 TEAE within a specific SOC and PT. The number (percentage) of subjects with TEAEs will also be summarized by maximum severity (mild, moderate, or severe). The number (percentage) of subjects with TEAEs will also be summarized by relationship to study drug (Yes [related] and No [not related]).

The number (percentage) of subjects with treatment-related TEAEs will be summarized by SOC and PT. Treatment-related TEAEs include those events considered by the investigator to be related to study drug. The number (percentage) of subjects with treatment-related TEAEs will also be summarized by maximum severity (mild, moderate, or severe).

AEs will be summarized by the following subgroups: region, concurrent AD medication use (yes, no), and clinical disease staging (MCI due to AD, early stage of mild AD).

The number (percentage) of subjects with TEAEs leading to death will be summarized by MedDRA SOC and PT for each treatment group. A subject data listing of all AEs leading to death will be provided. The number (percentage) of subjects with treatment-emergent serious adverse events (SAEs) will be summarized by MedDRA SOC and PT for each treatment group. A subject data listing of all SAEs will be provided. The number (percentage) of subjects with treatment-emergent non-serious AEs will be summarized by MedDRA SOC and PT for each treatment group. The number (percentage) of subjects with TEAEs leading to discontinuation from study drug will be summarized by MedDRA SOC and PT for each treatment group. A subject data listing of all AEs leading to discontinuation from study drug will be provided. The number (percentage) of subjects with TEAEs leading to interruption of study drug will be summarized by MedDRA SOC and PT for each treatment group. A subject data listing of all AEs leading to interruption of study drug will be provided. The number (percentage) of subjects with TEAEs leading to concomitant treatment administration will be summarized by MedDRA SOC and PT for each treatment group. A subject data listing of all AEs leading to concomitant treatment administration will be provided.

The number (percentage) of subjects with TEAEs of special interest will be summarized by MedDRA SOC and PT for each treatment group. TEAEs relating to abnormal dreams, nightmares, or sleep terror will be defined as TEAEs classified by the category recorded in Adverse event CRF or completing sleep/abnormal dream questionnaire. The number

(percentage) of subjects with TEAEs relating to abnormal dreams, nightmares, or sleep terror will be summarized by maximum severity (mild, moderate, or severe). The number (percentage) of subjects with treatment-emergent SAEs relating to abnormal dreams, nightmares, or sleep terror of clinical interest will be summarized. The number (percentage) of subjects with TEAEs relating to abnormal dreams, nightmares, or sleep terror of clinical interest leading to discontinuation from study drug will be summarized. The number (percentage) of subjects with treatment-related TEAEs relating to abnormal dreams, nightmares, or sleep terror will be summarized. The frequency, time to first event, and maximum AE duration of TEAEs relating to abnormal dreams, nightmares, or sleep terror will be summarized. Time to first event will be defined as time from first dose to earliest relevant AE. Maximum AE duration will be maximum time from AE start date to AE end date in each subject.

The number (percentage) of subjects with TEAEs of cognitive special interest will be summarized by MedDRA SOC and PT for each treatment group using the following PT (Table 1).

Table 1. PT for TEAE of cognitive special interest

Amnesia	Delirium	Global Amnesia	Senile Dementia
Amnesia NEC	Dementia	Illogical Thinking	Senile Dementia NOS
Anterograde Amnesia	Dementia Alzheimer's type	Memory impairment	Short-term memory Loss
Behavioral and psychiatric symptoms of Dementia	Dementia NOS	Mental impairment	Thinking abnormal
Cognitive deterioration	Dementia NOS Aggravated	Mental Impairment NOS	Thinking abnormal NEC
Cognitive disorder	Dementia of the Alzheimer's type NOS	Mental State Abnormal Aggravated	Thinking Slowed
Cognitive disorder NEC	Dementia with Lewy Bodies	Mental Status Changes	Transient Global Amnesia
Confusion	Disorientation	Mini-Mental Status Examination Abnormal	Vascular Dementia
Confusion aggravated	Disturbance in attention	Presenile Dementia	Vascular Dementia NEC
Confusional State	Frontotemporal Dementia	Retrograde Amnesia	

TEAEs of clinical interest will be defined as below.

- Lymphocyte Related Events: all preferred terms of lymphopenia, lymphocyte count abnormal and lymphocyte count decreased.

- Skin Related Events: all preferred terms under the High Level Group Term of epidermal and dermal conditions, High Level Term of urticarias and High Level Term of panniculitides.
- SAEs in Infections and Infestations SOC: only SAE and all preferred term under the SOC of infections and infestations.
- Weight Decrease Related Events: all preferred terms of weight decreased and abnormal loss of weight.

The number (percentage) of subjects with TEAEs of clinical interest will be summarized for each treatment group. The number of (percentage) of subjects with TEAEs of clinical interest will be summarized by time of occurrence (< 3 month, 3 to < 6 month, 6 to < 9 month, 9 to < 12 month, 12 to < 15 month, 15 to < 18 month, 18 month to more). The number (percentage) of subjects with TEAEs of clinical interest will be summarized by maximum severity (mild, moderate, or severe). The number (percentage) of subjects with treatment-emergent SAEs of clinical interest will be summarized. The number (percentage) of subjects with TEAEs of clinical interest leading to discontinuation from study drug will be summarized. The number (percentage) of subjects with treatment-related TEAEs of clinical interest will be summarized. The number (percentage) of subjects with TEAEs in OLE phase will be summarized by MedDRA SOC and PT on All Safety Subjects.

5.5.3 Laboratory Values

Laboratory results will be summarized using International System of Units, as appropriate. For all quantitative parameters, the actual value and the change from baseline to each postbaseline visit and to the end of treatment visit and 12 week Follow-up visit will be summarized by visit and treatment group using descriptive statistics. Qualitative parameters will be summarized using frequencies (number and percentage of subjects), and changes from baseline to each postbaseline visit and to end of treatment visit and 12 week Follow-up visit will be reported using shift tables. Percentages will be based on the number of subjects with both nonmissing baseline and relevant postbaseline results.

Laboratory test results will be assigned a low/normal/high (LNH) classification according to whether the value was below (L), within (N), or above (H) the laboratory parameter's reference range. Within-treatment comparisons for each laboratory parameter will be based on 3-by-3 tables (shift tables) that compare the baseline LNH classification to the LNH classification at each postbaseline visit and at the end of treatment visit and 12 week Follow-up visit. Similar shift tables will also compare the baseline LNH classification to the LNH classification for the highest and lowest value during the treatment period.

[Section 12.1](#) (Sponsor's Grading for Laboratory Values) presents the criteria that will be used to identify subjects with treatment-emergent markedly abnormal laboratory values (TEMAVs). Except for phosphate, a TEMAV is defined as a postbaseline value with an increase from baseline to a Grade of 2 or higher. For phosphate, a TEMAV was defined as a postbaseline

value with an increase from baseline to a Grade of 3 or higher. When displaying the incidence of TEMAVs, each subject may be counted once in the laboratory parameter high and in the laboratory parameter low categories, as applicable.

5.5.4 Vital Signs

Descriptive statistics for vital signs parameters (ie, systolic and diastolic BP, pulse, respiratory rate, temperature, weight), and changes from baseline will be presented by visit and treatment group.

In addition, frequency counts of clinically notable vital signs will be summarized by treatment group. [Table 3](#) presents the clinical notable ranges.

Table 3. Clinical Notable Ranges for Vital Signs

Vital Sign	Criterion for Low	Criterion for High
Pulse (bpm)	< 40	> 120
Temperature (°C)	< 36	> 38
Weight (kg)	< 45	> 100
Systolic BP	< 90	> 160
Diastolic BP	< 50	> 100

Weight increase ($\geq 7\%$) and weight decrease ($\geq 7\%$) will be summarized by visit and treatment group.

5.5.5 Electrocardiograms

Descriptive statistics for ECG parameters and changes from baseline will be presented by visit and treatment group. Shift tables will present changes from baseline in ECG interpretation (categorized as normal; abnormal, not clinically significant; and abnormal, clinically significant) to the end of treatment visit and 12 week Follow-up visit.

In addition, the number (percentage) of subjects with at least 1 post-baseline abnormal ECG result in corrected QT interval calculated using Fridericia's formula (QTcF) interval during the treatment period will be summarized. Clinically abnormal ECG results in QTcF interval will be categorized as follows:

Absolute QTcF interval prolongation:

- QTcF interval >450 msec
- QTcF interval >480 msec
- QTcF interval >500 msec

Change from baseline in QTcF interval:

- QTcF interval increases from baseline >30 msec
- QTcF interval increases from baseline >60 msec

Combined:

- QTcF interval >450 msec and QTcF interval increases from baseline >60 msec

5.5.6 Other Safety Analyses

As for Safety magnetic resonance imaging (MRI), findings about vasogenic edema and other abnormalities will be summarized by treatment group using frequencies (number and percentage of subjects). Shift tables will present changes from baseline in white matter disease to each visit and the end of treatment visit and 12 week Follow-up visit by treatment group. Descriptive statistics for total number of microhemorrhages will be presented by visit and treatment group.

The Columbia - Suicide Severity Rating Scale (C-SSRS) responses will be mapped to Columbia-classification algorithm of suicide assessment (C-CASA). The incidence of new or worsening suicidal ideation or suicidal behavior will be summarized by treatment group. Categorical variables will be summarized by number (percentage) of subjects. The clinical assessment of suicidal thinking and behavior will be summarized by visit and treatment group.

Additional information on AEs of possible drug abuse potential will be listed. Sleep/Dream questionnaire will be summarized by treatment group.

Cognitive decline will be assessed as a safety assessment, in addition to efficacy assessments. In addition, a greater than 8 point decrease in ADAS-cog word recall score from previous visit triggers an ADAS-cog RCI Alert. ADAS-cog word recall score is calculated by the summation of the words recalled from Word Recall Trial 1, Word Recall Trial 2, Word Recall Trial3, and Delayed Word Recall (Range: 0-40). The number of subjects with ADAS-cog RCI Alert triggered will be summarized by visit and treatment group.

Dermatology findings will be summarized by visit and treatment group.

Neurological examination will be summarized by visit and treatment group.

5.6 Pharmacokinetic, Pharmacodynamic, and PHARMACOGENOMIC/PHARMACOGENETIC ANALYSES

Pharmacokinetic Analyses

The PK Analysis Set will be used for the summaries of elenbecestat plasma and CSF concentrations.

Pharmacokinetic - Pharmacodynamic Analyses

The PK/PD relationship between CSF biomarker levels, and plasma PK parameters or CSF concentrations of elenbecestat will be explored graphically if a trend in biomarkers with time of treatment is noted

Additionally, the relationship between various PK parameters (eg, C_{max}) or CSF concentrations of elenbecestat and CDR scores (CDR-SB, CDR global score, and CDR Memory Box score) at 24 months (including both absolute score and the change from baseline), and the relationship between various PK exposure parameters or CSF concentrations of elenbecestat and the change

from Baseline for 24 months in ADAS-cog₁₄, and the MMSE, will be explored graphically if deemed necessary and only in case of a trend with time of treatment.

5.7 OTHER ANALYSES

No other analyses are planned.

6 INTERIM ANALYSIS

There is no interim analysis of efficacy, but there will be a futility analysis when 30% subjects have completed 24 months. The sponsor may stop the trial for futility with nonbinding futility boundary calculated using conservative O'Brien-Fleming boundary of Lan-DeMets alpha spending function with 30% information based on completers. If the actual percent information of the futility analysis is different from 30%, the futility boundary will be recalculated using the actual percent information at time of futility analysis. A blinded sample size re-estimation through estimated standard deviation based on blinded data prior to the completion of enrollment, will be performed if there is an indication that sample size assumptions need to be changed. This blinded sample size re-estimation could be performed based on signals from external studies or based on review of blinded data from this study prior to completion of enrollment. The standard deviation of the primary endpoint was estimated based on data from the ADNI study. It is possible that the standard deviation for the same endpoint in clinical trials may be larger than that from this observation study.

An independent DSMB will convene at regular intervals to monitor the overall safety of the study and to make recommendations to the sponsor related to study safety as appropriate. The DSMB will be asked to review the cumulative safety data up to the date identified to make a determination if the trial is safe to proceed unchanged or to provide recommendations to the Sponsor as to how to proceed. The study will proceed, including randomization of additional subjects, during DSMB safety reviews. DSMB reviews will then continue to occur at regular intervals. Details will be provided in the DSMB Charter.

7 CHANGES IN THE PLANNED ANALYSES

The following analyses will be added because they were focused on DSMB analyses.

- ADAS-cog₁₁
- TEAE by SOC/PT based on FDA-defined cognitive PTs
- Abnormal body weight change
- Summary of ADAS-cog RCI Alert Triggered by visit
- Subgroup analysis for very mild subjects defined as baseline CDR-SB \leq 1.5 and baseline MMSE \geq 27

The definition of time to worsening of CDR score by 24 months will be modified to use the date of second worsening instead of the date of first worsening in order to focus on sustained worsening.

The analyses to evaluate change from last dose will be added in CDR-SB, ADCOMS, ADAS-cog₁₁, ADAS-cog₁₄, MMSE, and ADAS-cog₁₄ Word List (immediate recall and delayed recall) instead of the analysis for 27 month in CDR-SB.

The following analyses will be conducted as one of sensitivity analyses instead of MMRM by censoring the data after change in concomitant AD medications to minimize the impact not only change in concomitant AD medications but also treatment discontinuation.

- MMRM by censoring the data after intercurrent events (i.e., treatment discontinuation or change in concomitant AD medications)

Several analyses for TEAEs relating to abnormal dreams, nightmares, or sleep terror and TEAEs of clinical interest will be added to evaluate safety profile more.

The following analyses will be removed from the planned analyses because there is a smaller sample size than originally planned.

- Analysis for amyloid PET SUVR, other biomarker endpoints, and exploratory endpoints by study level
- Analysis for CSF A β (1-x), CSF A β (1-42), and CSF A β (1-40) except summary statistics
- Statistical analysis for EQ-5D, QoL-AD, and Zarit's Burden Interview to compare elenbecestat 50 mg versus placebo
- Analysis for OLE data except specified in this SAP

The analyses for tau PET and CSF will be modified to include the assessments collected at early discontinuation visit as much as possible.

The following analyses will be reported separately from the CSR.

- Analysis for functional magnetic resonance imaging (fMRI)

8 DEFINITIONS AND CONVENTIONS FOR DATA HANDLING

8.1 DEFINITION OF BASELINE

The baseline value for efficacy, biomarker and safety will be defined as data collected prior to and/or on the date of first dose, usually the same day as the Day 1 (Visit 2). If there is more than one value on or before Day 1, the value closest to and prior to (including on) the date of first dose will be used as the baseline value.

8.2 DEFINITION OF VISIT WINDOWS

The protocol specified visits/weeks and corresponding time windows used for visit-wise analyses are presented in terms of days relative to the first dose.

Different assessment may have different visit schedule. A general rule for determining a time window for each scheduled visit is to split the two consecutive scheduled visits in the middle point of the two consecutive visits. For example, the time window for visit X is from the middle point between visit (X-1) and X (exclusive) to the middle point between visit X and (X+1) (inclusive). Table 4 shows the case in primary endpoint, as example. The details for other efficacy/biomarker/safety endpoints will be specified in the programming specification.

Table 4. Visit Windows for Primary Endpoint

Analysis visit	Target visit day	Analysis visit window
Baseline	1	The value closest to and prior to (including on) the date of first dose
Week 13 Day 85	85	[43, 134]
Week 27 Day 183	183	[135, 228]
Week 40 Day 274	274	[229, 319]
Week 53 Day 365	365	[320, 410]
Week 66 Day 456	456	[411, 501]
Week 79 Day 547	547	[502, 592]
Week 92 Day 638	638	[593, 683]
Week 105 Day 729	729	[684, 753]

In addition, the following visits will be assigned separately (for efficacy/safety endpoints) if last dose date is known

- Last on treatment: the last post-baseline assessment on or before last dose date. [except EQ-5D/QOL-AD/Zarit's Burden Interview/C-SSRS]

- End of treatment: the earliest assessment on or after last dose date and before last dose date + 56 days (inclusive) [except C-SSRS]
- 12 week Follow-up visit: the closest assessment to last dose date + 84 days after last dose date, but after last dose date + 57 days (inclusive) [except EQ-5D/QOL-AD/Zarit's Burden Interview/C-SSRS]

For efficacy endpoints, the assessments at early discontinuation from study drug, follow-up visits, clinical assessments at 12 and 24 months, unscheduled visits will be assigned to analysis visit using the same visit window rule.

For safety endpoints, the assessments after last dose date + 8 days (inclusive) will not be included in the visit-wise analyses except specific visit described above (the analysis flag should not be "Y"). If last dose date is missing, the assessment at early discontinuation from study drug, follow-up visits and unscheduled visits on or after early discontinuation from study drug or follow-up visits will not be included in the visit-wise analyses.

For biomarker endpoints, the following allowance after last dose date will be used. The assessments out of each allowance will not be included in the visit-wise analyses.

- Amyloid PET: last dose days + 28 days (inclusive)
- Tau PET: no limitation (all assessments will be included)
- CSF Ab(1-x), Ab(1-40), Ab(1-42): last dose days + 5 days (inclusive)
- Plasma Ab(1-x): last dose days + 5 days (inclusive)
- CSF total tau, p-tau, NFL, neurogranin: no limitation (all assessments will be included)
- Plasma NFL: last dose days + 28 days (inclusive)
- vMRI: no limitation (all assessments will be included)

If last dose date is missing, the assessment at early discontinuation from study drug, follow-up visits and unscheduled visits on or after early discontinuation from study drug or follow-up visits will not be included in the visit-wise analyses for amyloid PET, CSF Ab(1-x), Ab(1-40), Ab(1-42), plasma Ab(1-x), and plasma NFL.

If there are multiple assessments for one analysis visit, the following rules will be applied in order to select one assessment.

1. Pick the closest assessment to the target day
2. Pick the assessment at scheduled visit than unscheduled visit

- Pick the earliest assessment within the same visit (day)

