All subjects who discontinue study drug before reaching 12 months of treatment during the Core Study will also be asked to return to the clinic for a 12 month clinical assessment and then again at 24 months. Subjects who discontinued study drug between 12 and 24 months of treatment will be asked to return to the clinic for a 24 month clinical assessment.

Eligible subjects may enter the Extension Phase immediately following the completion of Visit 15 (final follow-up visit) of the Core Study. Subjects who are eligible to participate in the Extension Phase but who do not transition to the Extension Phase on the day of Visit 15 may enter the Extension Phase any time within 4 weeks of Visit 15. All subjects who enter the

Extension Phase will be treated with elenbecestat, including the subjects who received placebo during the Core Study. For all subjects, assessments performed at Visit 15 will serve as baseline values for the Extension Phase.

Figure 1 Study Design of E2609-G000-301/302

Elenbecestat = Test drug, PET = positron emission tomography, R = randomization.

- a: Subjects who participate in the optional longitudinal tau PET substudy will be permitted an additional window of up to 5 days (resulting in a total of up to 85 days) in order to accommodate the additional tau PET scan required to be performed during prerandomization. (revised per Amendment 05)
- b: The last day of the Core Study (Visit 15) is also the first day of the Extension Phase

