5.1.2 SECONDARY ENDPOINTS

The key secondary endpoints of the study are as follows

- Change from baseline in ADCOMS at 24 months in the combined studies
- Change from baseline in amyloid PET SUVR at 24 months for brain amyloid levels in the combined studies
- Change from baseline in amyloid PET SUVR at 24 months for brain amyloid levels in the individual studies

The other secondary endpoints of the study are as follows

- Change from baseline in the CDR-SB at 24 months for subjects enriched by baseline PET SUVR, eg, between 1.2 and 1.6, in the combined studies
- Change from baseline in the ADCOMS at 24 months for subjects enriched by baseline PET SUVR, eg, between 1.2 and 1.6, in the combined studies
- The rate of change over time (mean slope) based on CDR-SB score over 24 months in the combined studies

- Time to worsening of CDR scores by 24 months (eg, the worsening of global CDR score is defined as an increase from baseline by at least 0.5 points on the global CDR scale on 2 consecutive scheduled visits at which global CDR is undertaken) in the combined studies
- Time to conversion to dementia by 24 months for subjects who were not clinically staged as dementia at Baseline based on clinical diagnosis in the combined studies
- Change from baseline in CDR-SB at 27 months (ie, 24 months of treatment plus 3 months posttreatment follow-up) in the combined studies
- Change from baseline in ADAS-cog₁₄, MMSE, and FAQ at 24 months in the combined studies
- Change from baseline in ADAS-cog₁₄ Word List (immediate recall and delayed recall) at 24 months in the combined studies

Based on the DSMB analyses, the change from baseline in ADAS-cog₁₁ will be added as one of other secondary endpoints.

The following secondary endpoint will be added to evaluate the change after last dose instead of the change from baseline in CDR-SB at 27 months described above.

- Change from last dose to follow-up in CDR-SB, ADCOMS, ADAS-cog₁₁, ADAS-cog₁₄, MMSE, ADAS-cog₁₄ Word List (immediate recall and delayed recall) in the combined studies

As the study E2609-G000-301 and study E2609-G000-302 were terminated early, the sample size for amyloid PET SUVR is smaller than originally planned. Therefore the following key secondary endpoint will be removed.

- Change from baseline in amyloid PET SUVR at 24 months for brain amyloid levels in the individual studies

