The other continuous secondary efficacy endpoints will be analyzed using the same MMRM model as the primary efficacy analysis to compare elenbecestat 50 mg versus placebo on the FAS, using baseline value corresponding to the response variable in the model. These endpoints include:

- Change from baseline in the CDR-SB at 24 months for subjects enriched by baseline PET SUVR, eg, between 1.2 and 1.6, in the combined studies
- Change from baseline in the ADCOMS at 24 months for subjects enriched by baseline PET SUVR, eg, between 1.2 and 1.6, in the combined studies
- Change from baseline in ADAS-cog₁₁, ADAS-cog₁₄, MMSE, and FAQ at 24 months in the combined studies
- Change from baseline in ADAS-cog₁₄ Word List (immediate recall and delayed recall) at 24 months in the combined studies

The following amyloid PET mean composite SUVR in centiloid scale ([Adamczuk, 2019](#)) will be used to enrich the population, extrapolated from the 1.2 to 1.6 SUVR calculated for Florbetapir ([Dhadda, 2018](#)) : 37.234 to 119.522 (equivalent to 1.198633 to 1.667324 in Florbetaben and 1.212557 to 1.777799 in Flutemetamol) (Adamczuk [2019])

With regard to the change from baseline in ADAS-cog₁₄ Word List, it includes the immediate and delayed recall tasks, their scores will be part of the ADAS-cog₁₄ assessment (Item 1 and 4).

For ADAS-cog₁₁, ADAS-cog₁₄, MMSE, FAQ, and ADAS-cog₁₄ Word List (immediate recall and delayed recall), the MMRM analysis will be conducted on FAS, by censoring the data after intercurrent events (treatment discontinuation, and initiation/change of AD medications) as sensitivity analyses.

The MMRM using the change from baseline at last on treatment visit and 12 week Follow-up visit will be conducted based on the subjects in FAS who have the assessments at both visits to evaluate the change after last dose in CDR-SB, ADCOMS, ADAS-cog₁₁, ADAS-cog₁₄, MMSE, and ADAS-cog₁₄ Word List (immediate recall and delayed recall) instead of the analysis for the change from baseline in CDR-SB at 27 months. The same MMRM as the primary efficacy analysis (except excluding baseline by visit interaction) will be used with appropriate contrast to evaluate the difference between last on treatment visit and 12 week Follow-up visit by each treatment group.

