Subjects who discontinue study drug early must complete the ED Visit (within 7 days of the last dose of study drug) and the Follow-Up Visits (1 and 3 months after the last dose of study drug). These Follow-Up Visits will be conducted to monitor efficacy and safety parameters after early withdrawal from the study or discontinuation of study drug.

All subjects who discontinue study drug before reaching 12 months of treatment during the Core Study will also be asked to return to the clinic for a 12 month clinical assessment and then again at 24 months.

Figure 1 Study Design of E2609-G000-301

Elenbecestat (E2609) = Test drug, EoT = End of Treatment, R = randomization.

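### The change-after-last-dose contrast has no post-dose allowance or age limit on its start value and no upper bound on its 12-week follow-up value, so it can span far more than 12 weeks

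*SAP*

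**What the plan says.** SAP v2.0 replaces the 27-month CDR-SB analysis with a secondary endpoint that section 5.1.2 lists as "Change from last dose to follow-up in CDR-SB, ADCOMS" and further scales. Section 5.4.2 gives the method: "The MMRM using the change from baseline at last on treatment visit and 12 week Follow-up visit will be conducted" in FAS subjects who have both values, "with appropriate contrast to evaluate the difference between last on treatment visit and 12 week Follow-up visit by each treatment group". The model is the primary MMRM without the baseline-by-visit interaction.

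Section 8.2 defines the two visits:

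- **Start:** "Last on treatment: the last post-baseline assessment on or before last dose date". It has no post-dose allowance and no maximum age.
- **End, the 12 week Follow-up visit:** "the closest assessment to last dose date + 84 days after last dose date, but after last dose date + 57 days". It has a lower bound and no upper bound.

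The same section defines a separate End of treatment value, running from the last-dose date to +56 days. This contrast does not use it. Section 3.2 adds late off-drug visits: "All subjects who discontinue study drug before reaching 12 months of treatment during the Core Study will also be asked to return" at 12 and again at 24 months, and those who stop between 12 and 24 months are asked back at 24 months.

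**The concern.** The endpoint should show what happens to cognition and function once drug is withdrawn. That matters here because the DSMB form of 11 September 2019 reports detrimental trends on some cognitive measures by 18 months and a more consistent negative trend at 24 months.

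The start rule rejects an assessment made even one day after the last dose. It falls back to the previous visit, which for CDR-SB is about 13 weeks earlier on the Table 4 schedule. The decline between that visit and the last dose happened on drug but enters the contrast as post-dose change. The end rule can take a value from many months off drug and call it 12 weeks. Either way the interval varies between subjects, and the model has no term for time since last dose.

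On-drug decline before stopping offsets any recovery after it, so a real recovery could be hidden. Equally, a withdrawal worsening could be reported where there was only ordinary progression.

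**Working it through.** **Inputs**

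- CDR-SB target days: 85, 183, 274, 365, 456, 547, 638, 729 (section 8.2, Table 4). The first gap is 98 days and the rest are 91.
- Follow-up target: last dose + 84 days; floor +57 (section 8.2).
- Planned placebo change: 1.46 points at 24 months (section 4). Assumed linear from Day 1 to Day 729, this is 1.46 / 728 = 0.0020 points per day. It is used only to give a scale.

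**Formula**

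Span = (last dose − start assessment) + (follow-up assessment − last dose).

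**1. The plan's own figure.** With the start assessment on the last-dose date and follow-up at +84, span = 0 + 84 = 84 days = 12.0 weeks. Drift = 84 × 1.46 / 728 = 0.17 points. The label holds in this case.

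**2. Start rule, follow-up exactly at +84.** The longest on-schedule case has the last dose one day before the next target visit. A visit on the last-dose date would itself qualify, so the largest lag is the gap minus one day.

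| Visit gap | Lag before last dose | Span | Weeks | Drift (points) | Share of span before last dose |
|---|---|---|---|---|---|
| 91 days | 90 | 174 | 24.9 | 0.35 | 90/174 = 52% |
| 98 days (Day 85 to 183) | 97 | 181 | 25.9 | 0.36 | 97/181 = 54% |

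In these cases about half of the reported change precedes the last dose.

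**3. End rule, 12-week visit missed.** Closeness to +84 then selects whatever is left beyond the floor.

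- Start assessment Day 365, last dose Day 455, next assessment Day 729: 274 days off drug, and a span of 364 days (52 weeks).
- The longest on-target post-dose interval when only the 12-week visit is missed has its last dose on Day 309. The Day 365 assessment is then at +56, below the floor, so Day 729 is taken: 729 − 309 = 420 days. Drift over those days = 420 × 1.46 / 728 = 0.84 points.

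**4. Is it corrected elsewhere?** Under section 5.4.1 the model adjusts for baseline, region, staging, AD medication use and *ApoE4* status. None of these carries the interval length. Section 8.2 has no other cap on either side.

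**5. How the SAP treats other data.** Section 8.2 drops safety assessments from last dose + 8 days on, so it keeps those up to +7. Among the biomarkers it allows +5 days for plasma and CSF amyloid and +28 days for amyloid PET and plasma NFL. Only this contrast's start value has no allowance.

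**6. After the change.** With a start value 0 to 7 days after last dose and follow-up at +84, span = 84 − 7 to 84 − 0 = 77 to 84 days (11 to 12 weeks).

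**The case against.** The strongest reply concerns frequency. A subject assessed on the last-dose date and at +84 has exactly 12 weeks. The open upper end does no harm when the 12-week visit is attended, because the rule picks the value nearest +84, and section 3.2 requires follow-up of all subjects. All of this stands.

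Some stronger readings are tempting and are not supported:

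- **That most subjects are affected.** Early termination makes stopping between visits plausible, but the document gives no count.
- **That the early-discontinuation visit usually falls after the last dose and is lost.** The only timing rule is in the superseded v1.0 SAPs, where subjects "must complete the ED Visit (within 7 days of the last dose of study drug"; it gives no direction. The problem in section 8.2 does not depend on it.
- **That the average span is about 129 days.** That follows only if stopping is uniform between visits and no subject is assessed on the last-dose date because of stopping.
- **That an 18-month value (about 1.08 points) will be labelled 12 weeks.** That needs a second missed visit, the 12-month assessment, as well.
- **That the endpoint cannot answer its question.** Placebo follows the same windows, so its contrast shows the drift common to both arms.

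The placebo reference is only partial. The planned contrast is within arm. Setting the arms side by side also leaves in any difference in decline while still on treatment, because part of the interval precedes the last dose. If the timing of stopping or missed visits differs by arm, that adds bias; the document shows no such difference.

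An on-drug anchor is also a legitimate choice in itself, but it does not justify leaving the anchor's age unlimited.

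**Conclusion.** The point holds as a defect in two derivation rules. As written, the contrast can span 174 to 181 days with every visit on target, against 84 intended. Placebo drift over that span is about 0.35 to 0.36 points instead of 0.17. If only the 12-week visit is missed, the follow-up value can lie up to about 420 days after the last dose (about 0.84 points).

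These are upper cases, not averages. They rest on Table 4 timing for CDR-SB and on linear placebo decline; other scales may have other schedules.

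Severity is moderate. This is an other secondary endpoint, outside the testing hierarchy of section 5.3.3 and unadjusted for multiplicity. Neither window definition enters the primary or key secondary analyses.

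**What to change.** For this analysis only:

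1. Take as start value the assessment closest to the last dose and no later than last dose + 7 days, the cut-off already used for safety data. The existing End of treatment value is not a substitute: at its +56 limit only 84 − 56 = 28 days would remain before a follow-up at +84.
2. Cap the follow-up window, for example at last dose + 57 to + 111 days (84 ± 27). The exact ceiling is a judgement.
3. Summarise the actual start-to-follow-up interval by arm for each scale.
4. Apply a maximum look-back for the start value as a sensitivity analysis, not as an exclusion. Under uniform stopping between 91-day visits, a hard 6-week limit would remove about (91 − 42) / 91 = 54% of subjects with no assessment in the first 7 days after last dose.

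**Cost:** SAP wording and two derivation rules, with no new data. Some subjects without an eligible follow-up value leave this analysis, and a start value may be up to 7 days off drug. Subjects with no assessment near the last dose still have a long interval, which steps 3 and 4 make visible.
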